Lamzede is indicated in patients with alpha-mannosidosis. The marketing authorisation in the EU was granted for Lamzede with European Commission implementing decision of 23rd March 2018. Lamzede is the only authorised treatment for alpha-mannosidosis in the European Union (EU). Prior to its approval, treatment focused on the relief of symptoms, and prevention of complications and impairments, with treatments and procedures designed individually based on symptoms and age. Bone marrow transplantation has been used as a therapeutic strategy for alpha-mannosidosis, but comes with a risk of mortality and morbidity. Palliative treatments include physiotherapy, respiratory physiotherapy or antibiotic treatment for recurrent infections. Prevention of the disease is restricted to prenatal diagnosis and carrier identification.

7.2 Rationale

The Registry is being conducted as an EU Risk Management Plan (EU-RMP) Additional Pharmacovigilance Activities. Lamzede received Orphan Drug Designation in both the EU and the United States, and the marketing authorisation approval in the EU is sought under exceptional circumstances. In connection to Lamzede marketing authorization and its Risk Management Plan, the Alpha-mannosidosis registry is requested to obtain long term data on effectiveness and safety of treatment with Lamzede; furthermore, the Registry will expand the current understanding of alpha-mannosidosis by collecting natural history data, disease modifiers and confounder factors in alpha-mannosidosis patients despite the therapeutic treatment they are receiving.

This study will be conducted in compliance with the Declaration of Helsinki (1964 and amendments), current International Council for Harmonisation (ICH) E6 Good Clinical Practice (GCP) as far as applicable, in accordance with the obligation in the framework of a marketing authorisation granted

Clinical Protocol Number: CLI-LMZYMAA1-12	
Clinical Protocol Version Number: 8.0	Date: 01 February 2019

under exceptional circumstances (category 2 of studies in Good pharmacovigilance practices [GVP] Module V) and all other applicable laws and regulations.

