9.3.1 Demographic and Baseline Characteristics

After the patient, or parents or a legally acceptable representative according to local regulation, has provided signed informed consent and the patient has been included in the Registry, the following information will be reported in the eCRF for the baseline visit.

- Demographics (ethnicity, age, gender).
- Medical and disease history and concomitant illnesses includes collection of time to diagnosis and manifestations, infections/fractures (if any), blood genotype results, serum/leukocyte determination of disease activity level, residual enzymatic activity, occurrence of bone marrow transplantation and outcome, hepatic or renal insufficiency.
- Previous and concomitant medications, including Lamzede received in hospital or home infusion setting*.
- Previous and concomitant procedures.
- Physical examination (including ability to perform the endurance test).
- Vital signs [systolic (SBP) and diastolic blood pressure (DBP), pulse rate (PR)] and anthropometric measurements (weight, height, head circumference with rate of growth by gender and age when applicable).

*all available information regarding therapies received by the patient before inclusion in the current study

Clinical Protocol Number: CLI-LMZYMAA1-12

Clinical Protocol Version Number: 8.0

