9.7.4 Effectiveness Variables

Effectiveness will be assessed by:

• Oligosaccharides in serum (µmol/L)

Clinical Protocol Number: CLI-LMZYMAA1-12

Clinical Protocol Version Number: 8.0

- 3MSCT (step/min)
- 6MWT (m)
- 2MWT (m)
- FVC (as litre and as percentage of predicted)
- EQ-5D-5L
- Zarit Burden Interview
- CHAQ
- Rate and length of infections (requiring or not antibiotic)
- Serum IgG, IgA and IgM
- Rate of psychotic events
- Behavior Checklists: CBCL prescholar (1.5-5) and scholar (6-18); Adult Behavior Checklist (19-59)/ASR, Older Adult Behavior Checklist (60-and above).

All effectiveness variables will be summarised by means of descriptive statistics or frequency distribution, as appropriate. All variables (actual values and change from baseline, if applicable) will be presented by time point. In addition, mean and individual profiles by time will be produced.

Since alpha-mannosidosis presents as a multi-systemic disease, characterized by many clinical manifestations, a Global Treatment Response (GTR) will be evaluated by aggregating single endpoints in 3 disease relevant domains: pharmacodynamics (reduction of serum oligosaccharides), functional (3MSCT, 6MWT and FVC % of predicted) and quality of life (improvement in CHAQ Disability Index and VAS pain). Patients will be considered responders in one domain if the Minimal Clinical Important Difference (MCID) established for each endpoint from proxy diseases will exceeded in at least one endpoint of the domain; GTR will be reached by patients responding in at least 2 domains.

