At the time of planning this registry, adopted MCID are: oligosaccharides below 4 umol/L, increase of 7 steps/minute for 3MSCT (proxy: MPS IV A), increase of 30 meters for 6MWT (proxy: Pompe disease), increase of 10% for FVC (proxy: Pompe disease), decrease of 0.13 for CHAQ DI (proxy: Juvenile Arthritis) and of 8.2% for CHAQ pain (as in paediatric rheumatology). However, taking into account the length of this registry and the disease characteristics, if new scientific factors (i.e. knowledge about alpha-mannosidosis, clinical guidance) emerge the criteria used to establish the GTR may be reviewed and additional criteria may be added (like, but not limited to, EQ-5D-5L and serum IgG). The Global Treatment Response rate after 3 years of Lamzede treatment in naïve patients able to perform the functional tests will be evaluated. The proportion of responders and the corresponding exact (Clopper-Pearson) two-sided 95% confidence interval (CI) will be presented.

Effects of baseline characteristics will be evaluated by means of regression/logistic models including:

- age subgroup (<18 years, \geq 18 years),
- gender (male, female),
- genotype by subcellular localization of the protein (Genotype Group 1, Genotype Group 2, Genotype Group 3, as defined by Borgwardt et all., 2015)
- baseline residual enzymatic activity (<10 nmol/h/mg, 10 to <15 nmol/h/mg, \geq 15 nmol/h/mg)
- baseline CHAQ Disability Index (0|-|1, 1-|2, 2-|3)

as covariates.

Clinical Protocol Number: CLI-LMZYMAA1-12	
Clinical Protocol Version Number: 8.0	Date: 01 February 2019

Comparison with control group will be done descriptively, provided that a minimum number of nontreated patients with adequate data will be enrolled. If data will allow, Global Treatment Response after 3 year will be analysed comparing the two groups using propensity score (PS) analysis. The PS will be calculated as the predicted probability of Lamzede-treated vs non-treated patients from a logistic regression. This score represents the "propensity" for an observation to be in a treatment group or the other. The logistic regression model will include the following confounding factors as explanatory variables:

- age subgroup (<18 years, \geq 18 years),
- gender (male, female),
- genotype by subcellular localization of the protein (Genotype Group 1, Genotype Group 2, Genotype Group 3, as defined by Borgwardt et all., 2015)
- baseline residual enzymatic activity (<10 nmol/h/mg, 10 to <15 nmol/h/mg, \geq 15 nmol/h/mg)

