- baseline CHAQ Disability Index (0-1, 1-2, 2-3)

The distributions of each confounding factor as well as of the calculated PSs (Lamzede-treated vs non-treated) will be displayed graphically for both groups and their similarity evaluated.

In addition, depending on the outcome of interest and available sample size, subgroup analyses may be performed and results will be presented and regarded as descriptive. Further exploratory analyses will be developed as necessary and fully described in the SAP.

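### The propensity model for the exploratory treated-versus-untreated GTR comparison omits bone marrow transplantation and five of the six baseline GTR components, and the planned balance plots would not show an imbalance in them

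*Protocol*

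**What the plan says.** Section 9.7.4 makes the between-group analysis conditional: "If data will allow, Global Treatment Response after 3 year will be analysed comparing the two groups using propensity score (PS) analysis". The covariate list is not left open: "The logistic regression model will include the following confounding factors as explanatory variables". Five factors follow: age (below 18, 18 and over), gender, genotype group (three), residual enzymatic activity (three bands) and "baseline CHAQ Disability Index (0-1, 1-2, 2-3". The same section then plans graphs, by group, of the listed factors and of the score. Only further exploratory analyses are passed on to the SAP.

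On transplantation, Section 7.1 states: "Bone marrow transplantation has been used as a therapeutic strategy for alpha-mannosidosis". Table 1 in Section 9.2.6 collects it under medical and disease history. Sections 9.3.1 and 9.7.3 both name "occurrence of bone marrow transplantation and outcome" among the baseline items. Section 9.2.3 has no exclusion criteria. In Section 9.7.1 the No-Lamzede effectiveness set is defined only by time off Lamzede.

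On the outcome, GTR combines a pharmacodynamic domain (serum oligosaccharides) with two others: "functional (3MSCT, 6MWT and FVC % of predicted) and quality of life (improvement in CHAQ Disability Index and VAS pain". The rule is: "GTR will be reached by patients responding in at least 2 domains". The limits begin: "adopted MCID are: oligosaccharides below 4 umol/L, increase of 7 steps/minute for 3MSCT". The first is a level; the other limits in that paragraph are changes.

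**The concern.** A propensity score balances only what is put into it, apart from whatever the entered variables happen to carry with them. Two kinds of recorded variable are missing here.

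The first is another disease-directed treatment. A transplanted patient who is off Lamzede counts as non-treated, with no restriction and no adjustment, so the comparator may mix untreated natural history with post-transplant course.

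The second is the baseline value of most of the outcome components. Baseline oligosaccharides matter most, because that response limit is an absolute level. A patient already below it who stays there can meet the pharmacodynamic domain without any change, and then needs only one more domain for GTR.

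At stake is the only adjusted between-group GTR analysis in the protocol. The balance graphs could look acceptable on the five listed factors while the groups differ on the omitted ones.

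**Working it through.** **The plan's own figure.** Section 9.5 gives exact 95% interval widths of 0.239 to 0.199 for 70 treated patients with GTR 0.60 to 0.80. With lower limit Beta(0.025; x, n-x+1), upper limit Beta(0.975; x+1, n-x), n = 70 and x = 70p, all five rows reproduce to three decimals (for example 0.476 to 0.715 at 0.60). The rows for 0.65 and 0.75 use non-integer counts, 45.5 and 52.5. This table concerns the single treated group and is not affected by the point made here.

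**Covariates against recorded variables.**

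| Variable | Scheduled at baseline | In propensity model |
|---|---|---|
| Bone marrow transplantation | yes | no |
| Serum oligosaccharides | yes | no |
| 3MSCT | yes | no |
| 6MWT | yes | no |
| FVC % predicted | yes | no |
| CHAQ VAS pain | yes (CHAQ) | no |
| CHAQ Disability Index | yes (CHAQ) | yes, three bands |

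One of the six GTR components is in the model and five are not. All are collected only where routine practice supplies them (Table 1, footnote 7).

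**Model size** (levels minus 1 for each factor, intercept not counted).
- As planned: 1 + 1 + 2 + 2 + 2 = 8.
- Planned bands plus transplantation: 9. Plus the five missing baselines as linear terms: 14.
- Age, enzyme activity and CHAQ Disability Index continuous: 1 + 1 + 2 + 1 + 1 = 6. The saving is one parameter each from enzyme activity and CHAQ Disability Index. Adding transplantation and baseline oligosaccharides gives 6 + 2 = 8.

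The protocol gives no number of untreated patients. Assuming 10 to 40, and taking them as the smaller group, patients per parameter are:
- 8 parameters: 10/8 = 1.25 to 40/8 = 5.0
- 9 parameters: 10/9 = 1.1 to 40/9 = 4.4
- 14 parameters: 10/14 = 0.7 to 40/14 = 2.9

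**Possible effect of transplantation.** All inputs are assumed. Let pu and pt be the transplanted fractions of untreated and treated patients, and d the change in GTR probability that goes with transplantation. The shift in the untreated rate relative to the treated rate is (pu - pt) × d. With pu from 0.1 to 0.5, pt from 0 to 0.05 and d from -0.2 to +0.4, the extremes are (0.5 - 0) × (-0.2) = -0.10 and (0.5 - 0) × 0.4 = +0.20. This is a crude shift, before any adjustment through the five listed factors.

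**Possible effect of baseline oligosaccharides.** Let q and r be the functional and quality-of-life response probabilities, assumed independent and each between 0.3 and 0.5.
- Pharmacodynamic domain met: GTR = 1 - (1 - q)(1 - r), from 1 - 0.7 × 0.7 = 0.51 to 1 - 0.5 × 0.5 = 0.75.
- Domain not met: GTR = q × r, from 0.3 × 0.3 = 0.09 to 0.5 × 0.5 = 0.25.

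Whether this domain is met without any change can therefore decide much of the GTR result for a patient.

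**The case against.** The comparison is modest by design. Section 9.7.4 makes it conditional, and Section 9.1 says that the expected untreated pool does not support a control group and allows only a descriptive, exploratory comparison. Section 9.9 acknowledges bias from self-selection without a randomised control and commits reports to describe it. These points stand and limit how much depends on the covariate list.

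Imbalance would not necessarily go unseen. Transplantation is among the baseline summaries (Section 9.7.3), and effectiveness variables are presented as actual values by time point. That helps, but Section 9.7.3 does not specify summaries by group, and the check tied to the propensity analysis covers only its own covariates.

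The small untreated group is the strongest objection to adding terms, and it stands against adding all six. It does not stand against a model that remains at 8 parameters, or against wider balance displays, which use none.

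Section 9.7.4 also describes the pharmacodynamic domain as a reduction. If a reduction were required as well as the level, the argument on baseline oligosaccharides would weaken; the stated limit does not require one.

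A reader might infer more than the documents support:
- **That the comparison is shown to be biased.** No transplantation frequency or baseline difference between the groups is given, and genotype, enzyme activity and CHAQ Disability Index may carry part of any severity difference.
- **That transplanted patients would respond often and so hide a Lamzede effect.** No response rate after transplantation is given. The functional and quality-of-life limits are changes, so the benefit of a transplant before baseline may already be in the starting values.
- **That baseline function drives the decision to start Lamzede.** No section says so; the protocol leaves treatment to the physician and routine practice.

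**Conclusion.** The point holds in a limited form. Section 9.7.4 fixes a propensity model without prior bone marrow transplantation and without five of the six baseline GTR components, all scheduled for baseline collection where routine practice supplies them. The exploratory comparison is therefore open to residual confounding by recorded factors, and the planned balance plots would not reveal it. Transplantation and baseline oligosaccharides are the omissions to address first.

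Size and direction are unknown. The range of -0.10 to +0.20 rests wholly on assumed transplantation frequencies and effects and only shows that either sign is possible. The primary single-group GTR rate and its exact interval do not depend on the propensity model. This is a low-cost improvement to a secondary, conditional analysis, not a defect in the primary result.

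**What to change.** In Section 9.7.4:
- Add prior bone marrow transplantation (yes/no) to the propensity model, or run the comparison with and without transplanted patients.
- Add baseline serum oligosaccharides where numbers allow. Entering age, enzyme activity and CHAQ Disability Index as continuous terms keeps the model, with both additions, at 8 parameters.
- Extend the planned balance displays to transplantation and to baseline oligosaccharides, 3MSCT, 6MWT, FVC % predicted and CHAQ pain.
- State residual confounding as a limitation. The Annex 2 checklist at present refers both its discussion and methods of adjustment to N/A, which should be brought into line with the planned propensity analysis.

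The cost is wording only, since no new data item is needed. The drawbacks are that some patients drop out of the model where a routine-care baseline oligosaccharide value is missing, that continuous terms assume a linear logit, and that leaving out transplanted patients in one of the two runs shrinks an untreated group already expected to be small.

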Lamzede (velmanase alfa, henceforth referred to as Lamzede) is a recombinant human lysosomal alpha-mannosidase product, developed as an intravenous enzyme replacement therapy (ERT) for the treatment of alpha-mannosidosis. The safety and efficacy of Lamzede in adults and children (\geq 6 years old) has been evaluated in 33 patients (20 males and 13 females; 19 children [paediatric group, aged younger than 18 years] and 14 adults; median age 17.1 years, range 6.0-35 years) in five clinical studies (three exploratory Phase I to IIb studies, one Phase III pivotal study and one Phase III long-term efficacy and safety evaluation (rhLAMAN-10) in all patients previously enrolled in clinical trials with under-treatment data for up to 48 months).

The rhLAMAN-10 open-label, uncontrolled, phase III study encompassed an integrated database created by pooling cumulative databases from all studies with Lamzede together with an additional long-term assessment endpoint. Statistically significant improvements were detected in serum oligosaccharide levels, 3-minute stair climb test (3MSCT) and pulmonary function over time, up to the last observation. The effects of Lamzede were more evident in patients younger than 18 years. Descriptive evidence of improvement was also documented in several additional clinical endpoints, including serum immunoglobulin G (IgG), Bruininks-Oseretsky Test Of Motor Proficiency–2nd Edition (BOT-2) subdomains and Childhood Health Assessment Questionnaire (CHAQ) Disability Index, CHAQ visual analogue scale (VAS) Pain, European Quality of Life Five Dimension Five Level Scale (EQ-5D-5L) Health Index. A progressive improvement from baseline was also evident in the 6-minute walk test (6MWT). For further details, refer to the Lamzede Summary of Product Characteristics (SmPC).

A multi-domain post-hoc responder analyses was conducted across the pharmacodynamics (serum oligosaccharide response only), functional (3MSCT, 6MWT and Forced Vital Capacity (FVC) % predicted) and quality of life (CHAQ disability index and CHAQ VAS pain) domains.

A clinically significant response for each domain was claimed when at least one parameter of the domain improved beyond the proposed MCID.

In the overall responder analysis, a patient was qualified as responder to treatment if response criteria was reached in at least two domains. The alpha-mannosidosis Response Model generated as part of this approach is depicted in Figure 1.

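### The exploratory propensity-score comparison of three-year GTR adjusts for recorded age only through one cut at 18 years, which would leave part of any smooth age confounding in place

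*Protocol*

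**What the plan says.** Section 9.7.4 of the protocol carries the same five factors in two lists.

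- The first list belongs to models of prognosis: "Effects of baseline characteristics will be evaluated by means of regression/logistic models including" the five factors as covariates.
- The second belongs to the treated-versus-untreated contrast: "If data will allow, Global Treatment Response after 3 year will be analysed comparing the two groups using propensity score (PS) analysis". For the score, "The logistic regression model will include the following confounding factors as explanatory variables".

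In both lists age appears as "age subgroup (<18 years, \geq 18 years"). Residual enzymatic activity is cut at 10 and 15 nmol/h/mg. The disability score is banded: "baseline CHAQ Disability Index (0-1, 1-2, 2-3"). The distributions of each factor and of the score are then to be plotted for both groups and compared.

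Age itself is collected. Section 9.3.1 lists "Demographics (ethnicity, age, gender"), and section 9.7.3 summarises it. Section 7.1 describes the 33 earlier trial patients ("median age 17.1 years, range 6.0-35 years"; 19 of them under 18) and reports that "The effects of Lamzede were more evident in patients younger than 18 years". Section 9.1 expects few untreated patients, with different clinical features, and limits the between-group comparison to a descriptive, exploratory one.

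**The concern.** The sole purpose of the propensity score here is to remove confounding, and the plan names age as a confounder. A two-level term treats a child of 6 and one of 17 as exchangeable, and likewise a 19-year-old and a 35-year-old. Section 7.1 describes a disease that worsens over decades, so response could well vary with age inside each class. If treated and untreated patients differ in age inside the classes, the adjusted GTR difference keeps part of the age effect while being reported as adjusted.

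The coding is written into the protocol, so an analysis plan that follows it inherits the problem. A graphical balance check on the listed two-level factor can compare the share under 18, but it cannot show age differences within each class.

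The CHAQ banding raises a similar point. A band is 1 unit wide and the response threshold in section 9.7.4 is a fall of 0.13, so one band spans 1/0.13 = 7.7 thresholds. A patient at 0 cannot fall by 0.13 and one at 0.9 can, yet both sit in the lowest band.

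**Working it through.** The protocol gives no figure for residual confounding, so there is none to reproduce. It also gives no registry age distribution, no age difference between groups, no shape for the age effect and no method for using the score. These are assumptions below and are varied.

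**Inputs from the protocol.** Cut at 18 (section 9.7.4). Median age 17.1, range 6.0-35, and 19/33 = 57.6% under 18 in the earlier trials (section 7.1). No age limit in the registry (sections 9.2.2 and 9.2.3).

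**Closed form.** With a linear age effect and a small group difference, the share of age bias left after one cut is 1 minus the share of the age variance that lies between the two classes. With p the proportion under 18 and z its normal quantile:

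- normal age: 1 - φ(z)²/[p(1-p)]
- uniform age: 1 - 3p(1-p)

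| Proportion under 18 | Normal | Uniform |
|---|---|---|
| 0.50 | 1 - 0.1592/0.25 = 36.3% | 1 - 3 × 0.25 = 25.0% |
| 0.576 | 37.2% | 1 - 3 × 0.2443 = 26.7% |
| 0.30 or 0.70 | 42.4% | 37.0% |
| 0.20 or 0.80 | 51% | 52% |

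**Stratifying on under 18 against 18 or over, large samples.** Group ages were centred on 17.1 and shifted apart by 2, 4 or 8 years.

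- Normal, lognormal or gamma age: 31-43% left with a linear outcome, 29-37% with a logistic outcome.
- Uniform age with a pure location shift: 45-50% left.
- Response changing only as a step at 18: 0% left.

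**Inverse-probability weighting from a logistic score.** Treatment odds were log-linear in age and no drug effect was assumed. The response probability followed logit = 1.5 - 0.08 × (age - 18).

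| Assumed ages | Left with the cut at 18 | Left with the cut plus a CHAQ class correlated 0.5 with age |
|---|---|---|
| Truncated normal or lognormal, 6-35 | 32-33% | 30-31% |
| Two-piece uniform, 6-35, median 17.1 | 25-26% | 23-24% |
| Wider range, 4-60 | 40-41% | 35-36% |

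With age entered continuously the residual was -0.1% to 0.1% in every scenario. That is a best case, because assignment was generated as log-linear in age.

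**In percentage points of GTR.** Multiply the crude bias by the share left. The smallest case is 0.0166 × 0.323 = 0.5 points. The largest with ages 6-35 is 0.0898 × 0.263 = 2.4 points. The largest with ages 4-60 is 0.2001 × 0.401 = 8.0 points.

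**The case against.** The strongest reply is that the impact is small. The comparison is conditional on the data and is labelled exploratory, and untreated patients will be few. Suppose 70 treated and 15 to 30 untreated patients, all with 70% response. The 95% half-width for the difference is then 1.96 × √(0.21/70 + 0.21/15) = 26 points, falling to 1.96 × √(0.21/70 + 0.21/30) = 20 points. A bias of 0.5 to 8 points lies well inside that. The only comparative figures in the protocol are 87% against 30% at 12 months (section 7.1), a gap of 57 points. This stands as a limit on importance. It does not remove the flaw: this is the only adjusted treated-versus-untreated comparison of GTR in the plan.

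A reader might also infer more than the documents support:

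- **A fixed share of bias.** The share left depends on the age distribution and on the shape of the effect, and the protocol states neither for the registry. It reports age differences only across the cut at 18 (for example, 100% paediatric against 71% adult response at last observation), so it does not demonstrate a gradient within either class.
- **A median split in the registry.** This is shown only for the 33 earlier patients. The registry has no age limit, and the GTR analysis is confined to treatment-naive patients.
- **Proven confounding.** A stronger drug effect in younger patients is effect modification. Confounding also requires age to differ between the groups and to affect response without the drug.
- **A biased treatment contrast from the baseline-characteristics models.** Those models are not described as comparing treated with untreated patients. There, coarse coding loses information.
- **A balance check that would look perfect.** Groups that differ in the share under 18 would show it. The check is blind only within classes.

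**Conclusion.** The point holds for the propensity-score comparison. The plan names age as a confounder, records it, and then reduces it to one cut. If age acts smoothly on response and differs between groups, roughly a quarter to a half of the age confounding would remain. The figure is about 36-37% for normal age with the cut near the median, somewhat lower where another covariate tracks age (23-36% in the weighted scenarios), and about 0% if response changes only at 18. All of these rest on assumed age distributions.

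No comparable figure can be given for enzymatic activity or CHAQ DI, because nothing in the protocol shows how patients fall across those bands. The primary effectiveness estimate, a single-group GTR proportion with an exact interval, is not affected. The change is worth making before comparative data accrue, but the point does not threaten the study's main result.

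**What to change.** In the propensity model of section 9.7.4:

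- Enter age at time zero of the comparison as a continuous term, with a simple check for curvature.
- Enter baseline CHAQ DI as a continuous term. Do the same for residual enzymatic activity where assay values are comparable across sites. It is not among the centrally measured markers, so comparability has to be confirmed first; otherwise keep its bands.
- Assess balance on the continuous values.
- Keep under 18 against 18 or over, and the bands, for descriptive and subgroup tables.

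The same coding would recover information in the baseline-characteristics models.

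The cost is wording only, since the variables are already in the data collection. The listed coding uses 1 + 1 + 2 + 2 + 2 = 8 coefficients. Continuous terms for all three variables use 1 + 1 + 2 + 1 + 1 = 6, or 7 if a curvature term for age is needed. The downside is that a functional form is assumed for each continuous term.
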